- **Feasibility and tolerability of the interventions** assessed by enrollment and retention numbers, protocol related adverse events (AE's), and questionnaires assessing satisfaction, quality of life and mood.
- Adherence to interventions assessed both with self-report and with the use of a smartphone application in conjunction with continuous glucose monitoring.

Secondary Outcomes:

- Weight (scale) and body composition (DXA) obtained at baseline (prior to the weight loss intervention), at 12 weeks (following the weight loss intervention), and at a 6mo follow-up time point.
- Physical activity assessed by accelerometry
- Free-living sleep patterns assessed by wrist actigraphy
- Objective (in-laboratory) sleep recording using Compumedics Inc Siesta digital sleep recorders
- Meal timing and energy intake assessed by photographic food records
- Patterns in 24h glucose assessed by continuous glucose monitors over 7 days before and after the weight loss intervention
- Questionnaire based measures of appetite
- HqbA1c and lipids
- Resting metabolic rate and nocturnal energy metabolism by indirect calorimetery

B. Description of Population to be Enrolled:

Inclusion criteria.

- Adult males and females with a BMI of 27-45 kg/m² and weight stable over the previous 6 months;
- Age, 18-50 years old;
- Passing medical and physical screening, and analysis of blood and urine screening samples:
- Typical eating duration >12 hours per day (assessed by questionnaires);
- Own a smartphone
- Reside or work within approximately 30 minutes driving distance of CU-AMC (potential
 participants living outside of this driving distance could be included in the study at the PIs
 discretion).
- For participants in the optional Reproductive Hormone Sub-study: females, age 18-40, with regular menstrual cycles (between 18-40 days).

Exclusion criteria.

- Pregnancy or lactation for women (women who are >6 months postpartum with no plans of becoming pregnant in the next year and who are not currently lactating can be included; oral contraceptives will be allowed if medication has been consistent for the prior 6 months)
- Postmenopausal women (menopausal status will be assessed during the history and physical, with requirement of self-reported regular menstrual cycles for the last year; women who have undergone hysterectomy but with ovaries in place who continue to have regular menstrual symptoms can be included)

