Dietary and Activity Prescriptions. Both groups will focus on caloric restriction to decrease overall EI. Participants will be given a personalized calorie goal based on their measured RMR. If RMR by indirect calorimetry and by Mifflin St-Jeor equation differ by >10%, then the average of the 2 values will be used. This estimated RMR will be reduced by 10% and then rounded to the nearest 100 kcal

Suggested macronutrient content (55% carbohydrates, 15% protein, 30% fat) will be the same for both groups. Participants in the RCD group will not be given any specific instruction regarding timing of food intake. Participants in the RCD+TRF group will be instructed to eat only during a window of 10 hours, starting within 3 hours of waking. They will also be instructed in specific strategies to support TRF including: strategies to deal with hunger outside eating windows, distraction techniques, and choosing a balanced diet/appropriate portions during feeding windows. All participants will be counseled on the importance of PA for weight loss and will receive a recommendation to perform 150 min/wk of PA.

Self-Reported Dietary Adherence, Effort, and Self-Efficacy: At weeks 4, 8 and 12, participants will be asked to rate on a 1-10 Likert scale: 1) how adherent they were to prescribed study diet over the past week, 2) how hard was it to adhere to prescribed study diet over the past week, and 3) how likely they feel they can adhere to prescribed diet for the next month³⁰. These questionnaires will also be administered monthly from month 4 through 9 to determine whether participants have continued to follow their prescribed dietary pattern. In addition, participants will be asked to use the Meal Logger app (Cohorts 1 and 2) or Google Voice at weeks 4 and 8, and monthly between months 4 and 9 in order to objectively assess adherence to the dietary intervention.

Intervention Safety and Tolerability: Participants will be asked to report AEs to study staff as they occur, to be reported to our IRB as per institutional guidelines. We will collect additional parameters to assess tolerability at week 12 and at the 6 month follow up visit. Quality of life (QOL) will be assessed with the RAND-36^{49,50} physical and mental health component summary score. Mood state will be assessed with the Profile of Mood States 2 (POMS-2)⁵¹⁻⁵³. Eating behaviors will be assessed with the Three Factor Eating Questionnaire (TFEQ)⁵⁴.

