Intervention Acceptability: Satisfaction with both the standard RCD and RCD+TRF program intervention will be assessed at week 12 and month 9 with a questionnaire that asks participants to rate on a 1-10 Likert scale how satisfied they were with specific domains of the intervention. The major domains that will be assessed are satisfaction with: 1) ability to adhere to caloric restriction and time restriction (for RCD+TRF group), 2) content of the dietary support curriculum, 3) content of the exercise support curriculum, 4) group meeting frequency and structure, and 5) weight loss achieved to date. Participants will also be asked in open-ended fashion to provide feedback on each domain of the intervention. We will also assess intervention acceptability by comparing the frequency of protocol related AE's, requirement for protocol modification, and attrition between groups.

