In addition, at the end of the intervention, participants in both the TRF and RCD groups (n=6-8 per group) will be asked to participate in focus groups led by [name], a licensed clinical health psychologist with experience developing heath focused behavioral interventions and conducting focus group research. The participants will be required to fill out an additional consent form. If the study team is unable to meet with them in person to obtain consent, then a virtual consent will take place via ZOOM. The goal of the focus groups will be to obtain more specific information about their perceptions of, and experiences with, the intervention. Participants will specifically be asked to discuss, via open-ended inquiry and discussion: 1) aspects of the intervention itself that were difficult or relatively easy to follow; 2) barriers that limited their adherence or satisfaction; 3) beneficial aspects of the intervention; 4) factors that facilitated their ability to adhere to the intervention; 5) aspects that they would change and their recommended changes. To obtain a more complete understanding of the participants' experiences, extensive efforts will be made to include individuals who were non-adherent or dropped out of the interventions. A research assistant will attend the focus groups to act as a scribe, and the sessions will also be recorded using an audio recording device which will be later used to transcribe the entire session. Once the recording has been transcribed, the audio recording will be deleted. Data in response to the open-ended queries will be analyzed by the focus group leader using primarily inductive procedures, searching for themes that could inform intervention refinement in advance of a larger clinical trial. The focus groups will last 60-90 minutes and will be conducted at the Anschutz Health and Wellness Center.

In case of situations in which in-person classes cannot be held (i.e., due to concern for transmission of disease during the COVID-19 global pandemic), meetings will be held virtually via Zoom. Zoom is a HIPAA compliant web and video conferencing platform. All participants will be provided with a link to join the meeting and instructions regarding optimal conditions in which to join the meeting (i.e., a quiet location with minimal distractions and ability to devote full attention to the meeting).

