Defining and reporting serious adverse events (SAEs). We will utilize the Common Terminology Criteria for defining Adverse Events (CTCAE). Adverse events will be graded as mild (Grade 1), moderate (Grade 2), severe (Grade 3), or life-threatening (Grade 4), with specific parameters according to the organ system involved. We will promptly notify the IRB (within 5 days of the occurrence) when unexpected SAEs occur, defined as death (Grade 5), life threatening illness, hospitalization or prolongation of hospitalization, congenital anomaly/birth defects, and persistent/significant disability. The IRB requires that any SAE that is unexpected and related or possibly related to the research intervention be reported. SAEs that are unrelated to the research intervention do not have to be reported to the IRB. Risks that are described in the protocol and consent do not have to be reported promptly to the IRB unless they occur more frequently or are more serious than expected. One exception to this rule is in the case of a death. All deaths must be reported, whether or not the death was related to the research.

Withdrawals and terminations. All withdrawals and terminations will be reviewed by the researchers involved in this proposed study and I on a case-by-case basis. The data will be scrutinized separately to assessment for association of the interventions with a specific adverse outcome. An individual subject may be terminated from the study based on the criteria listed below. Any subject that is terminated from the study based on these criteria will be reported to the COMIRB during the annual continuing review.

- Request by the volunteer to leave the study
- Evidence of deliberate non-compliance
- Alcohol abuse; illicit drug abuse
- Development of a chronic condition (e.g. Grave's disease, hypothyroidism, rheumatoid arthritis, congestive cardiac failure, or neurological disorders such as MS or stroke) likely to impact upon metabolic variables, requiring medications likely to impact upon metabolic variables, or impair the ability of the subject to participate
- Development of an acute condition (e.g. myocardial infarction, major depression, accidents outside of the study resulting in physical impairments) likely to impact upon metabolic variables, requiring medications likely to impact upon metabolic variables, or impair the ability of the subject to participate Subjects will be reviewed on a case-by-case basis and will be reported to the Data Safety Officer.

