Statistical Analysis: Efficacy Testing: Baseline demographic characteristics will be summarized by treatment groups using descriptive statistics. Any imbalance between groups will be examined using two-sample t-tests and Fisher's exact tests as appropriate. The primary analysis will use the ITT principle to test our study hypotheses under practical and realistic conditions when not all participants follow or complete the program. All randomized participants will be analyzed. A linear mixed effect model (LMM) will serve as the primary method to handle missing values. The normality assumptions will be evaluated and transformations used (e.g. square root and log) as appropriate. Change in weight is the primary outcome variable and others will be secondary outcomes. Consequently, no adjustment for multiple outcomes will be applied. P-values <0.05 will be considered significant. No interim analysis is planned. Any imbalance in baseline characteristics between groups that could potentially be a confounding factor for the outcome will be adjusted for in the statistical model (i.e., age, sex, level of PA achieved during intervention). Differences between groups in weight, fat mass, lean mass, MVPA, EI, sleep outcomes, and glucose variability will be compared using a LMM. Specifically, the test of time by group interaction will be used to assess efficacy. Pearson's correlations will be used to assess the relationship between sleep and nocturnal metabolism outcomes and longitudinal weight regain at 6 months. Variability of Major

Outcome Measures: Standard deviation and effect sizes will be determined based on the LMM model estimates to assist with planning the large-scale trial.

G. Summarize Knowledge to be Gained:

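### Undefined deliberate non-compliance is a ground for termination from the study, not just the program, so adherence, questionnaire and weight data can be lost for outcome-related reasons

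*Combined protocol and SAP*

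**What the plan says.** The rule is in Section IV.D, Data and Safety Monitoring Plan, under Withdrawals and terminations: "An individual subject may be terminated from the study based on the criteria listed below". One criterion is "Evidence of deliberate non-compliance". It stands in the same list as a volunteer's own request to leave. No definition, threshold, source of evidence or assessor is given. The research team reviews each case, and terminations are reported to the IRB at annual review. Nothing separates stopping the program from stopping follow-up.

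Other sections bear on this:

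- **Section IV.A, Primary Outcomes.** Feasibility is "assessed by enrollment and retention numbers", among other measures. Adherence to the interventions is the other listed primary outcome.
- **Section IV.C, Dietary and Activity Prescriptions.** Both arms have a calorie goal, but only RCD+TRF has an eating window: "Participants in the RCD group will not be given any specific instruction regarding timing of food intake".
- **Section IV.C, Self-Reported Dietary Adherence.** Ratings are due at weeks 4, 8 and 12 and are then "administered monthly from month 4 through 9 to determine whether participants have continued to follow their prescribed dietary pattern".
- **Section IV.C, Intervention Acceptability.** Acceptability is judged partly by comparing "requirement for protocol modification, and attrition between groups".
- **Section IV.C, focus groups.** The plan says that "extensive efforts will be made to include individuals who were non-adherent or dropped out of the interventions".
- **Section IV.F, Statistical Analysis.** Intention to treat is chosen for conditions "when not all participants follow or complete the program. All randomized participants will be analyzed". A linear mixed model (LMM) is the primary method for missing values.

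**The concern.** In this pilot, failure to follow the diet is a result. Adherence and retention are what the trial reports in order to decide whether RCD+TRF is ready for a larger study. A rule that lets the team end a participant's time in the study for non-compliance selects on that result.

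Three things are at stake. First, retention and the between-arm attrition comparison become partly an investigator decision. Use of the rule could differ by arm, because RCD+TRF participants have one more instruction to break. Second, adherence and satisfaction ratings would stop for the people they are most needed to describe, and non-adherent participants would be harder to reach for the focus groups. Third, weight data would be missing for a reason probably related to weight change. Data gathered before termination stay in the analysis, but a participant terminated before week 12 may have no post-baseline weight. The LMM is then valid only under missing at random. That is doubtful here, because adherence is not a named covariate and Section IV.F states no sensitivity analysis.

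**Working it through.** **Is follow-up kept after termination?** The rule ends participation in the study, by its own words. Section IV.C asks all participants for the 12-week assessments and all subjects for the 6-month ones, but does not say whether this includes people already terminated. The only stated effort to reach non-adherent or departed participants concerns the focus groups, with 6 to 8 people per group. No section of the protocol says that outcome collection continues.

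**What one early termination could cost.** Self-reported adherence is due 3 times by week 12 (weeks 4, 8, 12) and 6 times afterwards (months 4 to 9), so 3 + 6 = 9. Termination just after week 4 leaves 9 − 1 = 8 unobserved. Section IV.A schedules outcome weight at baseline, 12 weeks and 6-month follow-up, so both post-baseline weights could be lost as well.

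**The plan's own figures (Section IV.F).** The inputs are 60 participants randomized 1:1, 20% attrition, and SDs of 3.7 kg (RCD) and 4.2 kg (RCD+TRF).

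- Completers: 60 × 0.8 = 48, or 24 per arm. This matches the plan.
- Standard error of the difference: √(3.7²/24 + 4.2²/24) = √(31.33/24) = 1.14 kg.
- The stated 80% power at 3.5 kg does not reproduce exactly. With these inputs a two-sided t-test has 85.1% power at 3.5 kg, and 80% power is reached at 3.27 kg. The plan is on the cautious side, and this does not affect the present point.

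**Illustrative shift in an arm's mean weight change.** The assumptions are: k of 30 in one arm are terminated; they would have lost 0 kg; the others average −4.1 kg. The last figure is the plan's value for RCD; it has none for RCD+TRF. The shift is k/30 × 4.1.

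| k | Shift | Shift ÷ 1.143 kg |
|---|---|---|
| 1 | 1/30 × 4.1 = 0.14 kg | 12% |
| 2 | 2/30 × 4.1 = 0.27 kg | 24% |

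The shift makes that arm look better than it is. The LMM would remove it only so far as variables in the model explain the loss.

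**Attrition and retention.** This assumes the terminations come on top of the 20%; the plan does not say whether the 20% includes them.

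| k | Attrition in that arm | Overall retention |
|---|---|---|
| 0 | 6/30 = 20.0% | 48/60 = 80.0% |
| 1 | 7/30 = 23.3% | 47/60 = 78.3% |
| 2 | 8/30 = 26.7% | 46/60 = 76.7% |

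Overall retention stays above the plan's 70% bar in each row.

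**The case against.** The best defense is that the criterion is narrow. It says deliberate, and it sits in a safety plan next to alcohol and drug abuse. Everywhere else the protocol treats lapses as something to measure: it rates adherence monthly, seeks out non-adherent people for focus groups, and chooses intention to treat because some will not follow the program. On that reading, ordinary lapses from the calorie goal or window would never trigger termination. The rule is also permissive, each case is reviewed, and the IRB and Safety Officer are told. Silence about follow-up is not an instruction to stop it, and the consent form could carry terms on data after termination.

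Several points stand. The frequency is unknown and may be low. Section IV.E says that compliance is measured objectively only at baseline and 12 weeks; before then, detection rests mainly on logs and reports that participants supply. Different use by arm is plausible but not shown, since both arms have a calorie goal to ignore. The weight shift is small, and no feasibility threshold is crossed. Doubt about missing at random applies to any diet-related dropout, not only to this rule.

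The rest does not answer the point. Knowingly eating outside the window fits the words as written, and nothing in the protocol excludes it. Reporting a termination to the IRB or Safety Officer does not recover the data. The sections that treat non-adherence as an outcome show what the investigators want, and the termination rule as worded works against it.

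**Conclusion.** The concern holds, and the plan should be changed. The protocol permits termination from the study for a reason that overlaps a primary outcome, and does not provide for outcome collection afterwards. The main harm is to the adherence, retention and attrition results. Two terminations in one arm, on top of the assumed attrition, would raise its attrition from 20.0% to 26.7% by investigator decision, and each early one could lose most of that person's adherence record. The effect on weight is modest: 0.14 to 0.27 kg for one or two participants, at most about a quarter of the standard error. These sizes rest on assumed counts, zero weight loss in those terminated, and the RCD mean applied to either arm. The plan gives no expected number of terminations, so confidence that the rule would matter in practice is medium.

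**What to change.** Amend Withdrawals and terminations in Section IV.D as follows:

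- Non-compliance may end participation in the program, but not follow-up.
- Define deliberate non-compliance. State that missing the calorie goal or the eating window is an outcome to record and not a ground for ending follow-up.
- Continue to seek weight, food logs and questionnaires at the scheduled times unless the participant withdraws consent.
- Count these participants as non-adherent in the adherence analysis.
- Report investigator terminations by arm, separately from participant withdrawals.

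The cost is a short protocol amendment and continued contact with a few participants at visits that are already scheduled. Some of them may decline, so the change reduces outcome-related missing data but does not remove it.

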The question of whether when we eat is as important as how much remains unanswered and is critical in the development of future recommendations regarding body weight regulation. Altering meal frequency has been evaluated as a weight loss strategy due to epidemiological studies showing an inverse relationship between meal frequency and adiposity^{10,11}, but interventional studies have shown conflicting results, with no definitive evidence of differences in weight loss or metabolic risk factors¹²⁻¹⁵. Breakfast eating is also recommended due to evidence linking breakfast skipping with obesity¹⁶⁻²⁰. However, several interventional studies have failed to show weight loss with breakfast eating²¹⁻²³. On the other hand, in two weight-loss interventions, individuals who consumed more calories in the morning as compared to the evening lost more weight, even though both EI and self-reported PA were similar^{2,3}. In addition, food intake at night (as seen with shift work), is linked to obesity independent of EI²⁴.

There are physiologically plausible mechanisms by which restricting EI to a window aligned with the early part of the day (i.e. TRF) may enhance weight loss and result in more favorable metabolic outcomes. A number of metabolic systems are entrained to circadian rhythms, including hormone, lipid and glucose concentrations, intestinal lipid absorption, and autonomic nervous system activity²⁵. Restriction of EI to a window of time and/or extension of the fasting period may alter diurnal patterns and circadian rhythms in glucose and lipid metabolism in a manner that favors decreased obesity risk. In rodent studies, metabolic benefits were seen with a TRF protocol, despite equivalent EI of a high fat diet^{8,9}. Only two studies of TRF have been done in humans. Gill and Panda²⁶ studied 8 overweight men and women with habitual eating duration >14 hours who were asked to restrict EI to a self-selected 10-11 hour window. Subjects lost weight (-3.27 kg), despite the fact that they were not specifically told to decrease their EI. Similarly, LeCheminant et al²⁷ studied 29 healthy young men in a cross-over design with a period of night eating restriction (no EI from 1900 to 0600 hrs) vs control, without recommendation to decrease EI, and found a modest weight reduction after 2 weeks (-0.4 kg). However, these studies were small and not designed as weight loss interventions.

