E. Potential Scientific Problems:

Adherence to the TRF protocol: This will be the first study to our knowledge that will assess the feasibility of using TRF in the context of a reduced calorie diet for weight loss. We will objectively measure compliance to the protocol at baseline and 12 weeks using CGM and photographic time-stamped food logs but will otherwise not know whether subjects randomized to the TRF group were compliant to the protocol. To limit the extent of possible non-compliance to the TRF arm we decided on a shorter intervention for our first study. We are also using a high intensity behavioral support program that will meet weekly to discuss dealing with hunger/cravings or other challenges that might be associated with TRF. We will also ask participants to keep a log documenting daily feeding duration (first and last energy intake events) during all intervention weeks.

F. Data Analysis Plan:

Sample Size Justification:. We will aim to recruit 60 participants in two cohorts.. The sample size was determined for the primary outcome, change in body weight (kg) at 12 weeks. Assuming 20% attrition, we will be left with n=48, or n=24 subjects per group. To justify the sample size, we computed the detectable difference that we have 80% power for based on existing preliminary and published data. We will assume an alpha=0.05 and use two-sample t-tests. We assumed that the RCD group will have similar weight loss as has been shown previously with the standard Colorado Weigh curriculum, in which the mean \pm standard deviation (SD) weight loss using an intent-to-treat analysis at 12 weeks is -4.1 \pm 3.7kg⁵⁷. There are no prior relevant data for 12-week weight loss using TRF in the context of a weight loss intervention. However, prior data from the Gill and Panda study²⁶ of time restricted feeding without a weight loss intervention showed a mean weight loss at 16 weeks of -3.3 kg with a SD=3.4 kg. Given that we are combining the RCD and TRF treatments, the standard deviation is likely to be between 3.4kg and the sum of the variation of the RCD and

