time restricted studies (SD of the sum = $\sqrt{3.7^2 + 3.4^2} = 5.0 \text{ kg}$). In our calculation, we assumed for the time restricted treatment group (RCD+TRF) a SD in-between the above lower and upper bounds of SD at 4.2kg. With these SD's, we have 80% power to detect a difference in mean weight loss between the two treatment groups of 3.5kg. This is slightly larger than the Gill and Panda study, but well within the range of the confidence interval of their result. In addition, this calculation is quite conservative. We will have power of 80% to detect an even smaller difference in weight loss between the groups, because in the final analysis we will adjust for baseline weight, which reduces the SD's in each of the groups and allows us to have power to detect smaller differences. The intervention will be modified if we are unable to recruit 30 participants, retain >70% of participants, or perform outcome measures within a 2-week window of the indicated time points in >90% of participants.

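### The 3.5 kg said to be detectable with 80% power does not follow from the plan's own inputs, which give 3.27 kg; the efficacy test also does not name week 12

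*Combined protocol and SAP*

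**What the plan says.** Section IV.F, Sample Size Justification, names the quantity being sized: "The sample size was determined for the primary outcome, change in body weight (kg) at 12 weeks". From 60 recruited and 20% attrition, "we will be left with n=48, or n=24 subjects per group". The method is given as "We will assume an alpha=0.05 and use two-sample t-tests". The RCD SD is 3.7 kg, from an earlier run of the same behavioural programme. For RCD+TRF the plan takes "a SD in-between the above lower and upper bounds of SD at 4.2kg", the bounds being 3.4 and 5.0 kg. With those SDs it concludes that "we have 80% power to detect a difference in mean weight loss between the two treatment groups of 3.5kg".

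It then compares that difference with the earlier uncontrolled study of time-restricted feeding: "This is slightly larger than the" result of that study, though inside its confidence interval. Section IV.F gives that study's mean loss as 3.3 kg; section II gives "Subjects lost weight (-3.27 kg").

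The Statistical Analysis paragraph of section IV.F names change in weight as primary, without a time point, and says that "the test of time by group interaction will be used to assess efficacy" in a linear mixed model (LMM). Section IV.A schedules weight at baseline, 12 weeks and a 6-month follow-up.

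**The concern.** Every input to the detectable difference is stated except sidedness, so a reader should be able to reproduce 3.5 kg. Rounding cannot turn 3.27 into 3.5. The comparison with the earlier study rests on the same figure and so carries the error with it.

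The second issue is whether the test that decides efficacy is the test the trial was sized on. A t-test on week-12 change has one degree of freedom. A time-by-group interaction over three visits, with time categorical, has two. It asks whether the arms differ at week 12, at follow-up, or both. A difference confined to follow-up could make it significant, and it can have less power than the t-test for a week-12 effect.

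**Working it through.** **Inputs (section IV.F).** n = 24 per group (60 × 0.8 = 48, split 1:1); SDs 3.7 and 4.2 kg; alpha 0.05; power 80%; two-sample t-test. Sidedness is not stated and is taken as two-sided.

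**Attempt to reproduce 3.5 kg.**

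- SE = √((3.7² + 4.2²)/24) = √(31.33/24) = 1.143 kg; df = 46; two-sided critical t = 2.013.
- For 80% power the noncentral t needs difference/SE = 2.862, so the difference is 2.862 × 1.143 = **3.27 kg**. The Welch version also gives 3.27 kg, and the normal approximation 3.20 kg.
- At 3.5 kg, difference/SE = 3.063 and power is **85.1%**.

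**What would give about 3.5 kg?**

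| Change to the stated inputs | Difference |
|---|---|
| None | 3.27 kg |
| One-sided alpha 0.05 | 2.88 kg |
| SD 4.2 kg in both arms | 3.47 kg |
| RCD+TRF SD 4.71 kg | 3.50 kg |
| 21 per group (30% attrition) | 3.51 kg |
| 85% power | 3.50 kg |

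Each route to 3.5 kg replaces a stated input. The unstated sidedness is not the explanation, since a one-sided test moves further away. Nor is baseline adjustment, which the plan offers as a gain beyond 3.5 kg. Over the plan's own bounds for the RCD+TRF SD (3.4 to 5.0 kg), the difference runs from 2.94 to 3.63 kg.

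**Comparison with the earlier study.** Its loss was 3.27 kg (section II) or 3.3 kg (section IV.F), so 3.27 kg is about equal to it. With n = 8 and SD 3.4 kg, the 95% interval is 3.3 ± 2.365 × 3.4/√8, or 0.46 to 6.14 kg. The plan's statement that its difference lies well within that interval still holds.

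**The interaction read as a 2-df test.** Take complete data on 24 per group at both post-baseline visits and test the two changes from baseline jointly (Hotelling T², F with 2 and 45 df). Let d₁ and d₂ be the true differences at week 12 and follow-up, r the ratio of follow-up to week-12 SD, and ρ the correlation of the two changes. The noncentrality is

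λ = (d₁/SE)² + (d₂/(r·SE) − ρ·d₁/SE)²/(1 − ρ²).

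- The second term cannot be negative, so λ is at least (d₁/SE)² whatever r and ρ are. At d₁ = 3.27 kg the minimum is 2.862² = 8.19, giving power **69.7%** against 80% for the 1-df test.
- 80% power needs λ = 10.31. In that worst case d₁ = √10.31 × 1.143 = **3.67 kg**.
- The worst case is not the rule. Over r = 1 to 1.5 and ρ = 0.5 to 0.9 (assumed), equal 3.27 kg differences at both visits give 69.7% to 82.4%. If the week-12 difference has vanished by follow-up, power is 82% to nearly 100%.
- With d₁ = 0 and an assumed d₂ = 2 kg, the test is significant in 19.7% (r = 1.5, ρ = 0.5) to 94.5% (r = 1, ρ = 0.9) of trials, against 5% for the week-12 contrast. With d₂ = 1 kg the range is 8% to 39%.

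These are complete-case figures, like the plan's own, and not the exact power of the LMM.

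**The case against.** The strongest reply is that little depends on the number. The error is conservative. The 60 participants were not solved from 3.5 kg; the detectable difference was computed afterwards to justify them. Aim 1b says outright that the pilot lacks the power to detect weight-loss differences, and section IV.A lists feasibility, tolerability and adherence as primary, with weight secondary. Using the larger SD in both arms would give 3.47 kg, a plausible cautious simplification.

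All of this limits the importance and none of it makes 3.5 kg reproducible. The plan ties its figure to the two SDs it has just stated, and presents it as the sample-size justification. The equal-SD explanation remains a guess.

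On the interaction, it is fair to say that week 12 is fixed in the same section, that the sentence covers many outcomes, some of them measured only at baseline and 12 weeks (where the interaction already has one df), and that the plan never says time is categorical. Aim 1b also treats 12-week loss and later regain as separate questions. A significant result driven by follow-up would be detection of a real difference, not a false positive, though it would not answer the week-12 question. This stands: the second point is a gap in clarity and not a contradiction.

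**Conclusion.** The concern holds and is minor. The stated inputs give 3.27 kg at 80% power, or 85% power at 3.5 kg, so the published design figure is wrong as written, in the conservative direction. This rests only on the plan's inputs and a two-sided test. No sample size changes, and the trial is not undersized for 3.5 kg.

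The interaction point is secondary and depends on reading time as categorical over all three weight visits. On that reading, the floor of 70% power at 3.27 kg does not depend on the follow-up SD or correlation; the figures for a follow-up-only difference depend on assumptions the documents do not supply. An LMM yields a week-12 estimate on either reading. What is left open is which test decides efficacy.

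**What to change.** In the Sample Size Justification, restate the 80%-power difference as about 3.3 kg, or say that power at 3.5 kg is 85%, or state the inputs that produce 3.5 kg. If the figure becomes 3.3 kg, describe it as about equal to the earlier study's result.

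In the Statistical Analysis paragraph, name the primary test of efficacy on weight as the 1-df between-arm contrast in change from baseline to week 12, estimated from the LMM, and report the 6-month contrast separately. Carry into that paragraph the baseline-weight adjustment promised in the sample-size text, and specify it once: baseline either as one of the modelled responses, or as a covariate with post-baseline responses only.

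The cost is one number, one reworded comparison and two sentences. It needs no new data and no change in sample size.
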